17.4.5	Passing through the Small Bowel Distal to the Ligament of Treitz.....	61
17.4.6	Reaching the Terminal Ileum.....	62
17.4.7	Withdrawal Techniques	63
17.5	Retrograde Approach	65
17.5.1	Passing through the Colon	65
17.5.2	Eliminating a Loop	66
17.5.3	Passing through the Ileo-cecal Valve	68
17.5.4	Passing through the Small Bowel.....	69
17.5.5	Reaching the Proximal Jejunum.....	69
17.5.6	Withdrawal Techniques	70

Table of tables

Table 1	Precision of estimations of the rate of patients with at least one SAE	24
Table 2	List of study procedures	25
Table 3	List of changes CIP version 01 versus CIP version 02.....	35
Table 4	List of anticipated (Serious) Adverse Events	50

Clinical Investigation Plan

CIP Reference No.:2018-GI (OEKG) -01. The **SAMISEN** study - Final Version 02 - Date 23th April 2019

LIST OF ABBREVIATIONS AND DEFINITIONS

Abbreviation	Definition
ADE	Adverse Device Effect
AE	Adverse Event
ATC	Anatomical Therapeutic Chemical
BAE	Balloon assisted enteroscopy
CE	Commission Européen
CIP	Clinical Investigation Plan
CCI	Coordinating Clinical Investigator
CRF	Case Report Form
CRO	Contract Research Organization
CV	Curriculum vitae
DBE	Double balloon enteroscopy
DIMDI	German Institute for medical documentation and information
EC	Ethics Committee
ECG	Electrocardiogram
GCP	Good Clinical Practice
ICH	International Conference on Harmonization
ISF	Investigator Site File
PI	Principal Investigator
SADE	Serious Adverse Device Effect
SAE	Serious Adverse Event
SBE	Single balloon enteroscopy
SOP	Standard Operating Procedure
SDV	Source Data Verification
TMF	Trial Master File
U	Unit
WHO	World Health Organization

Clinical Investigation Plan

CIP Reference No.:2018-GI (OEKG) -01. The **SAMISEN** study - Final Version 02 - Date 23th April 2019

TRIAL SUMMARY

Title	Safety and Performance of the Motorized Spiral Endoscope (PowerSpiral) in Subjects indicated for small-bowel enteroscopy: A PMCF Registry.
Short Title or Acronym	The SAMISEN study (S afety and P erformance of the M otorized S piral E ndoscope)
Version/ Date	CIP#: 2018-GI (OEKG) – 01 Version 2.0 (23 April 2019)
Sponsor	OLYMPUS EUROPA SE & Co. KG [name]
Purpose	Demonstrate safety and clinical performance of the Motorized Spiral Endoscope (PowerSpiral) in daily medical practice.
Objective	Prospectively collect clinical data on the application of the Motorized Spiral Endoscope (PowerSpiral) in a typical clinical setting within the Intended Use.
Endpoints	
 • Diagnostic Yield: Defined as the percentage of procedures that either confirmed a diagnosis from previous studies, or established a new definitive diagnosis at the anatomical location identified in previous studies or findings that could explain the clinical symptoms • Therapeutic Yield: Defined as the percentage of patients with any endoscopic intervention / therapy with the exception of biopsies • Total procedure time: (starting with oral /anal insertion until final withdrawal of the device) • Total therapeutic intervention time • Total small bowel enteroscopy rate: Defined as complete evaluation of the small bowel either with a single approach or combined anterograde and retrograde approach (if complete small bowel enteroscopy is intended anyway) • Endoscopic success rate • Safety: Incidence (% of subjects) and frequency (no. of subjects) with device or procedure related Serious Adverse Events (SAEs) and Device Deficiencies (DD) observed during/after the procedure • User feedback and assessment of handling characteristics of the device
Study Design	International, multicenter, open label, non-randomized, prospective, observational study.
Sample Size	260 subjects will be enrolled into this registry including an expected rate of 5% of losses-to-follow-up during study conduct. The first 5 procedures for each investigator will be performed to get used to the device. Data on these “learning curve” procedures will be captured and analyzed separately. The dataset for final analysis (e.g. procedure time, rate of SAEs etc.) will include 260 cases from procedure #6 onwards in order to account for a learning curve effect. The sponsor plans to activate 12 sites with one or two investigators at each site. Each site shall enroll up to 22 subjects (notwithstanding the learning curve cases) to allow for the same quota per site. Overall approximately 335 subjects will be enrolled (including cases for the learning curve).

Clinical Investigation Plan

CIP Reference No.:2018-GI (OEKG) -01. The **SAMISEN** study - Final Version 02 - Date 23th April 2019

Timelines	Study Start (Enrollment of First Patient) is planned for May/June2019. Enrollment period: 1 year (until May/June 2020). Study closure: Q2/2020.
Investigation- al Device(s) used	Motorized Spiral Endoscope (PowerSpiral) INTESTINAL VIDEOSCOPE OLYMPUS PSF-1 in combination with SINGLE USE POWERSPIRAL TUBE DPST-1 used with the motor control unit POWERSPIRAL CONTROL UNIT PSCU.
Study Population	
Subjects with an indication for direct visualization of the small bowel which fulfil all inclusion and none of the exclusion criteria:
 
Inclusion criteria
 
 1. Signed informed consent 2. Patients with small bowel disease indicated for deep enteroscopy, including but not limited to: 
 • Gastrointestinal bleeding • Crohn's disease • Abdominal pain or chronic diarrhea • Large polyps (>10–15mm) in the jejunum and ileum in patients with Peutz–Jeghers syndrome • Nonresponsive or refractory coeliac disease • Results and hints from other preliminary investigations, e.g. small-bowel capsule endoscopy, small-bowel imaging examinations etc. which warrant further work-up with antegrade and/or retrograde enteroscopy of the small-bowel 
Exclusion criteria
 
In addition to be eligible for study enrollment a subject must not meet any of the exclusion criteria listed below.
 
 1. Age under 18 years 2. Female and of child-bearing age who is currently pregnant or planning to become pregnant within the study period 3. Any contraindication to standard enteroscopy (e.g. severe coagulopathy or known coagulation disorder; bowel obstruction / stenosis, stents or other instruments implanted in the intestinal tract, suspected GI perforation, esophageal or gastric varices, eosinophilic esophagitis) as judged by the investigator after careful individual risk assessment 4. Concurrent participation in another competing clinical study

Clinical Investigation Plan

CIP Reference No.:2018-GI (OEKG) -01. The **SAMISEN** study - Final Version 02 - Date 23th April 2019

Data Collection	
Each subject will undergo the following study visits:
 
 • Visit 1 – screening visit, inform potential subjects about the trial, obtain informed consent from subjects to participate in the study, check inclusion / exclusion criteria, collect data on medical history and concomitant medication. • Visit 2 - scheduled procedure: perform antegrade or retrograde or combined enteroscopy as planned. Provide feedback on the handling characteristics of the PowerSpiral enteroscope. • Visit 3 – (optional) second procedure: retrograde (or antegrade) enteroscopy as necessary. • Visit 4 – pre-hospital discharge visit: collect any (delayed) complication 														
Study Flow Chart	
  
 Patient selection	Visit 1	Visit 2	Visit 3 – (optional)	Visit 4	
   
  <pre> graph LR A{Patient scheduled for enteroscopy of small-bowel} -- yes --> B[Inclusion / Exclusion criteria] A -- no --> C[Exclusion] B -- yes --> D[Anterograde and/or retrograde enteroscopy as planned] B -- no --> C D -- yes --> E[Anterograde or retrograde enteroscopy if necessary] D -- no --> C E -- yes --> F[Final visit] E -- no --> C </pre> 	Screening visit	Scheduled procedure	Second scheduled procedure	Hospital discharge visit	
  
					Patient selection	Visit 1	Visit 2	Visit 3 – (optional)	Visit 4	<pre> graph LR A{Patient scheduled for enteroscopy of small-bowel} -- yes --> B[Inclusion / Exclusion criteria] A -- no --> C[Exclusion] B -- yes --> D[Anterograde and/or retrograde enteroscopy as planned] B -- no --> C D -- yes --> E[Anterograde or retrograde enteroscopy if necessary] D -- no --> C E -- yes --> F[Final visit] E -- no --> C </pre>	Screening visit	Scheduled procedure	Second scheduled procedure	Hospital discharge visit
Patient selection	Visit 1	Visit 2	Visit 3 – (optional)	Visit 4											
<pre> graph LR A{Patient scheduled for enteroscopy of small-bowel} -- yes --> B[Inclusion / Exclusion criteria] A -- no --> C[Exclusion] B -- yes --> D[Anterograde and/or retrograde enteroscopy as planned] B -- no --> C D -- yes --> E[Anterograde or retrograde enteroscopy if necessary] D -- no --> C E -- yes --> F[Final visit] E -- no --> C </pre>	Screening visit	Scheduled procedure	Second scheduled procedure	Hospital discharge visit											
Study Contacts															

Clinical Investigation Plan

CIP Reference No.:2018-GI (OEKG) -01. The **SAMISEN** study - Final Version 02 - Date 23th April 2019

1 BACKGROUND AND RATIONALE

Small bowel enteroscopy is usually performed in order to evaluate gastrointestinal bleeding, small bowel tumors, polyps, inflammatory or other small bowel diseases. Video capsule endoscopy, single- (SBE), double-balloon (DBE) or spiral enteroscopy are the most popular non-surgical endoscopic techniques in this context. Hereof the endoscopic approach offers additional diagnostic and therapeutic options as biopsies and direct therapeutic intervention is possible compared to capsule endoscopy. These enteroscopy systems – also called overtube-assisted enteroscopy (OAE) techniques - are used to visualize the small-bowel and proceed with a therapeutic intervention, either during the same or in a subsequent session. For example, the DBE utilizes distal and proximal balloons that can be inflated and deflated to “anchor” and move the bowel, thereby assisting the operator in advancing the endoscope while gathering the bowel onto the overtube shaft.

However, the SBE and DBE procedures are time consuming and usually require 2 operators to perform this kind of examination.

1.1 Description of the Investigational Device

The Motorized Spiral Enteroscope (INTESTINAL VIDEOSCOPE OLYMPUS PSF-1 and SINGLE USE POWERSPIRAL TUBE DPST-1) in conjunction with the motor control unit (POWERSPIRAL CONTROL UNIT PSCU) now offers a new technology which combines the advantageous options of enteroscopy with a faster and less invasive approach. The intended use of this CE-certified medical device (PowerSpiral) is to examine the lumen of the small intestine to provide clear images for diagnostic and therapeutic purposes in the management and treatment of small-bowel disease.

The system is similar to other currently marketed endoscopes and incorporates a flexible insertion tube, light source, digital imaging, and channels for passing accessories for sample collection or therapeutic interventions. In contrast to the predecessor a novel user-controlled motor rotates a special spiral cuff (SINGLE USE POWERSPIRAL TUBE DPST-1) located on the endoscope's insertion tube (POWERSPIRAL CONTROL UNIT PSCU). Rotation of this cuff, which has soft spiral-shaped “fins”, pleats the small bowel on to the endoscope's insertion tube, thereby allowing rapid and atraumatic access into deeper regions of the small bowel. The Rotating speed is 30 rpm and the Rotation torque is controlled mechanically until torque limit is reached (until a limiting function is activated).

With this new medical device system deep enteroscopy allows complete visualization of the small bowel. The motorized PowerSpiral can be used for either antegrade or retrograde approach according to the operator's preference or individual patient anatomy. The new device shall

Clinical Investigation Plan

CIP Reference No.:2018-GI (OEKG) -01. The **SAMISEN** study - Final Version 02 - Date 23th April 2019

contribute to easier and faster disease clarification and necessary therapeutic interventions in all areas of the small intestine.

The study investigators shall have considerable experience in deep enteroscopy. The study team will undergo special training (arranged by the Sponsor) to become comfortable with all handling characteristics of this novel device. The product and procedure training is mandatory prior to enrolling the first study subject and will be documented accordingly.

1.2 Justification for the Design of the Clinical Investigation

Deep enteroscopy is well established with Balloon assisted enteroscopy procedures, however there is a need for innovative and faster methods, less resource utilization which at the same time provide more comfort for the patients.

Currently available and published data for PowerSpiral was collected by means of Investigator Initiated Trials (Mans et al. 2018; Neuhaus et al. 2016; Beyna et al. 2018; Beyna 2018). With this Olympus sponsored Registry further data about performance and safety for this new medical device will be collected in a larger patient population. Obtained safety data will be compared to data published in respective guidelines or literature.

This study will be performed in parallel to the European market launch of this new medical device. It is a registry study with a CE marked medical device whose application within the intended use will be captured. The registry and does not impose any additional procedure or risk to the patient as we strive to document daily clinical routine. Therefor this study is observational (non-interventional) in nature.

For the same reason inclusion criteria are kept as broad as possible. In summary all patients are eligible where the physician realizes an indication for deep enteroscopy for further diagnostic or therapeutic work up. The exclusion criteria will only affect patients under the age of 18 years and pregnant women. Otherwise clinical judgement of the treating physician is the only relevant and leading reason for exclusion. Of course giving signed informed consent by all study subjects is a prerequisite for participation in this "registry".

For this study approximately 12 European sites will be recruited that offer deep enteroscopy to their patients. This international multi-center setup will give a more representative picture and avoid a single-site bias. Furthermore enrollment will be completed earlier compared to a single center approach.

The prevailing complications of a deep enteroscopy are pancreatitis, perforation, bleeding and adverse events associated with sedation or anesthesia (Aktas et al. 2010; Akarsu et al. 2014; Akerman and Cantero 2009; Arulanandan et al. 2016; He et al. 2013; Moeschler and Mueller 2015). Generally these are independent if the procedure was performed as a diagnostic or therapeutic procedure however the complications rate is usually higher in interventional cases (Rondonotti et al. 2018).

Clinical Investigation Plan

CIP Reference No.:2018-GI (OEKG) -01. The **SAMISEN** study - Final Version 02 - Date 23th April 2019

The main objective of the SAMISEN study is to assess the performance and safety of diagnostic and therapeutic procedures with the newly designed Olympus Motorized Spiral Enteroscope (INTESTINAL VIDEOSCOPE OLYMPUS PSF-1 and SINGLE USE POWERSPIRAL TUBE DPST-1) system in combination with the motor control unit (POWER SPIRAL CONTROL UNIT PSCU). All Serious Adverse Events (SAE) observed in this study will be documented so the overall SAE rate as well as the number of individual types of complications (bleeding, pancreatitis etc.) can be calculated.

The very recent publication of Rondonotti (Rondonotti et al. 2018) for device-assisted enteroscopy for diagnosis and treatment of small-bowel disorders represents an excellent source for comparison. Hence this study is designed as a prospective study without control group. The resulting SAE rate will be compared to the historical data from this ESGE Technical Review (Rondonotti et al. 2018).

The performance will be characterized by calculating the Diagnostic and Therapeutic Yield, Total Procedure Time, time needed for Therapeutic Intervention, Total Small Bowel Enteroscopy Rate and user feedback on device handling.

1.3 Risks and Benefits

All patients present a medical challenge which requires a deep enteroscopy for diagnostic and/or therapeutic purpose(s). Independent of the clinical study this kind of examination has certain clinical risks associated with such a procedure which must be balanced again other treatment alternatives (e.g. open surgery). After careful consideration of risk and benefits the investigator decided to proceed with direct visualization of the small bowel and adequate therapeutic inventions. Due to the non-interventional character of this study (i.e. registry) no additional protocol driven procedure besides medical standard are required. In summary the potential risk a subject enrolled into the SAMISEN study is considered identical to the risks he/she would be facing without participating in this study.

The complication rate associated with endoscopic procedures is usually low. Experience with deep enteroscopy of the small-bowel has been published for SBE and DBE. Distribution and incidence of complications depend whether it was a diagnostic or therapeutic approach. For therapeutic procedures tissue usually is removed or biopsies obtained which carries a higher complication rate compared to purely diagnostic procedures. A deep enteroscopy examination is performed with sedation or anesthesia, depending on the hospital standards. Any anesthesia carries a certain risk for the patient, especially if multi-morbidity is present.

Section 11.4 provides a list of all potential (S)AEs that have either been observed during or after deep enteroscopy with PowerSpiral conducted in a clinical study setting or are anticipated. There is no additional device related new risk identified that was not already anticipated for its predecessor.

Clinical Investigation Plan

CIP Reference No.:2018-GI (OEKG) -01. The **SAMISEN** study - Final Version 02 - Date 23th April 2019

The overall risk / benefit ratio for this clinical investigation is assumed to be in the same acceptable range of established balloon assisted methods of deep enteroscopy. As mentioned earlier this registry does not impose any additional “protocol driven” interventions or examinations therefore the procedural risk to which a patient will be exposed to should be very similar to the risk in case he/she would not have agreed to participate in this study

Clinical Investigation Plan

CIP Reference No.:2018-GI (OEKG) -01. The **SAMISEN** study - Final Version 02 - Date 23th April 2019

2 TRIAL OBJECTIVES

2.1 Objective

The main objective of this registry is to collect data on the safety and performance of the new motorized PowerSpiral device when used as intended by the manufacturer. It is assumed that the new device and its safety profile is non-inferior to preceding generations of balloon assisted enteroscopes.

As clinical performance and efficacy is equally important for the user this study also collects efficacy and handling data of the new device.

With this registry OLYMPUS complies with Post-Market Clinical Follow-up (PMCF) requirements.

Clinical Investigation Plan

CIP Reference No.:2018-GI (OEKG) -01. The **SAMISEN** study - Final Version 02 - Date 23th April 2019

3 DESIGN OF THE CLINICAL INVESTIGATION

3.1 General

3.1.1 Design Overview

SAMISEN is an international, multicenter, non-randomized, prospective, observational open label (registry) study examining the CE- marked PowerSpiral (OLYMPUS PSF-1, SINGLE USE POWER SPIRAL TUBE and motor control unit POWER SPIRAL CONTROL) device. (For justification of the study design please refer to section 1.2)

3.1.2 Randomization and Blinding or Assignment of Investigational Device

SAMISEN is designed as a prospective single-arm trial without control group or randomization. All subjects enrolled will undergo at least one procedure with the Motorized Spiral Endoscope (PowerSpiral). There may be a second (optional) procedure depending on investigator's discretion usually because the region of interest could not be reached during the first endoscopy. Subsequent endoscopic procedures are often characterized by a switch in direction (a first antegrade route may be followed by a second retrograde approach or vice versa). From a study perspective and because only part of the subjects will receive a second procedure this additional procedure is called "optional" to indicate that it is not required by protocol but will only be performed if considered necessary by the treating investigator.

3.1.3 Variables in the Clinical Investigation

It is a prospective and observational Registry without any additional procedure beyond clinical practice. The small-bowel enteroscopy has to be performed according the medical standard. Serious Adverse Events (SAE) and Device Deficiencies (DD) must be documented.

The main safety endpoint is a combined one, capturing all SAEs / DDs captured during the study period. The definition is:

- **Safety:** Incidence (% of subjects) and frequency (no. of subjects) of device or procedure related Serious Adverse Events (SAEs) and Device Deficiencies (DD) observed during/after the procedure.

As main efficacy endpoint we will determine in how many cases the suspected anatomical target lesion can be reached. The definition is:

- **Diagnostic Yield:** Defined as the percentage of procedures that either confirmed a diagnosis from previous studies, or established a new definitive diagnosis at the anatomical location identified in previous studies or findings that could explain the clinical symptoms (Sethi et al. 2014; Prachayakul et al. 2013; Lenz, Roggel, and Domagk 2013; Sanaka et al. 2012).

Clinical Investigation Plan

CIP Reference No.:2018-GI (OEKG) -01. The **SAMISEN** study - Final Version 02 - Date 23th April 2019

Further efficacy endpoints cover performance aspects of the device. The definitions are:

- **Therapeutic Yield:** Defined as the percentage of patients with any endoscopic intervention / therapy with the exception of biopsies. (Sethi et al. 2014; Prachayakul et al. 2013; Sanaka et al. 2012).
- **Total procedure time:** the time from oral (anal) insertion until withdrawal of the device.
- **Total therapeutic intervention time:** The part of the procedure dedicated to therapeutic maneuvers (biopsies will not be considered here).
- **Total small bowel enteroscopy rate:** Defined as complete evaluation of the small bowel either with a single approach or combined anterograde and retrograde approach (if complete small bowel enteroscopy is intended anyway (Committee et al. 2015; Gerson et al. 2015).
- **User feedback** and judgment of handling characteristics and other aspects.

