4.1.2 Efficacy evaluation

The efficacy endpoints are defined as follows:

- **Reaching the anatomical region of interest:** The rate of successfully reaching the suspected anatomical target region (either by antegrade or by retrograde route) compared to all attempts represents the **anatomical success rate**.
- **Therapeutic Yield:** Defined as the percentage of patients with any endoscopic intervention / therapy with the exception of biopsies. (Sethi et al. 2014; Prachayakul et al. 2013; Sanaka et al. 2012).
- **Total procedure time.**
- **Total therapeutic intervention time:** period in min dedicated to therapeutic intervention(s).
- **Total small bowel enteroscopy rate:** Defined as complete evaluation of the small bowel either with a single approach or combined anterograde and retrograde approach (if complete small bowel enteroscopy is intended anyway (Committee et al. 2015; Gerson et al. 2015).
- **User feedback** and judgment of handling characteristics and other aspects.

Clinical Investigation Plan

CIP Reference No.:2018-GI (OEKG) -01. The **SAMISEN** study - Final Version 02 - Date 23th April 2019

- User feedback and assessment of handling characteristics and other logistical aspects regarding:
 - Handling of PowerSpiral
 - Instrument insertion of PowerSpiral
 - Precision of positioning during therapy of PowerSpiral
 - Time needed for procedure of PowerSpiral
 - Staff and resource needed for procedure of PowerSpiral

No hypothesis testing will be performed for any efficacy endpoint.

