2.4 Primary and secondary variables

Primary efficacy variable:

The rate of serious adverse events during and after enteroscopy will constitute the primary endpoint for this study.

Secondary efficacy variables:

- Reaching the anatomical region of interest: The rate of successfully reaching the suspected anatomical target region (either by antegrade or by retrograde route) compared to all attempts represents the endpoint 'anatomical success rate'.
- Therapeutic yield: Defined as the percentage of patients with any endoscopic intervention / therapy with the exception of biopsies. (Sethi et al. 2014; Prachayakul et al. 2013; Sanaka et al. 2012)
- Total procedure time: Period in minutes needed to complete the procedure.
- Total therapeutic intervention time: Period in minutes dedicated to therapeutic intervention(s).
- Total small bowel enteroscopy rate: Defined as complete evaluation of the small bowel either with a single approach or combined anterograde and retrograde approach (if complete small bowel enteroscopy is intended anyway (Committee et al. 2015; Gerson et al. 2015).
- Diagnostic Yield (i.e. diagnosis, that explains findings from previous imaging or establishes a new diagnosis, that could explain clinical symptoms, that indicated PSE)
- User feedback and judgment of handling characteristics and other aspects: User feedback and assessment of handling characteristics and other logistical aspects regarding:
 - Handling of PowerSpiral
 - Instrument insertion of PowerSpiral
 - Precision of positioning during therapy of PowerSpiral
 - Time needed for procedure of PowerSpiral
 - Staff and resource needed for procedure of PowerSpiral
- Serious adverse events (PS product related)
- Adverse events during enteroscopy procedure and adverse events (PS product related)

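### The protocol announces reaching the target as the main efficacy endpoint but defines it as diagnostic yield, and no section settles which rate is the main efficacy result

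*Protocol*

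**What the plan says.** Protocol section 3.1.3 introduces the endpoint with "As main efficacy endpoint we will determine in how many cases the suspected anatomical target lesion can be reached". It then announces a definition, and the only one given is diagnostic yield: "Defined as the percentage of procedures that either confirmed a diagnosis from previous studies, or established a new definitive diagnosis". That definition goes on to tie a new diagnosis to the location found in earlier work-up, and it also admits findings that could account for the symptoms. The remaining endpoints are set apart by "Further efficacy endpoints cover performance aspects of the device", and neither the reach rate nor diagnostic yield is among them.

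Protocol section 4.1.2 opens its list of efficacy endpoints with "The rate of successfully reaching the suspected anatomical target region (either by antegrade or by retrograde route) compared to all attempts", which it names the anatomical success rate. Diagnostic yield is not in that list. The section closes with "No hypothesis testing will be performed for any efficacy endpoint".

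The SAP states in section 2.4 that "The rate of serious adverse events during and after enteroscopy will constitute the primary endpoint for this study". It places both the anatomical success rate and diagnostic yield under "Secondary efficacy variables", with no order of importance.

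**The concern.** A plan that names a main efficacy endpoint should let the reader work out, before any data are seen, which number that will be. Here the introductory sentence points to one number and the definition to another, and the later sections do not settle it.

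The study is open-label with a single arm and no efficacy test, so the label attached to a rate is one of the few efficacy choices left open. If the label is fixed only after both rates are known, the more favourable one can be presented as the main result. Protocol section 2.1 treats performance as no less important to users than safety, and section 14 gives the sponsor the coordination of publications. The label is therefore likely to be used.

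**Working it through.** **1. The sections side by side**

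| Place | Reach rate | Diagnostic yield | Ranking |
|---|---|---|---|
| Protocol summary, Endpoints | absent (only an undefined endoscopic success rate) | first in list | none stated |
| Protocol 1.2, performance list | absent | first in list | none stated |
| Protocol 3.1.3 | in the introductory sentence | in the definition | both tied to the main efficacy endpoint |
| Protocol 4.1.2 | first in list | absent | none stated |
| SAP 2.3 | first secondary objective | absent | secondary |
| SAP 2.4 | listed | listed | both secondary |
| SAP 3.6 | rate with 95% Clopper-Pearson interval | difference of two patient proportions | none stated |

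Only protocol section 3.1.3 uses the label main efficacy endpoint, and it attaches that label to both quantities.

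**2. Are they the same quantity?** Take *n* procedures with a common denominator and split them four ways: *a* reached with a diagnosis, *b* reached without one, *c* not reached (or no target set) but with an explanatory finding, *d* neither.

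- Reach rate = (*a* + *b*)/*n*
- Diagnostic yield = (*a* + *c*)/*n*
- Reach minus yield = (*b* − *c*)/*n*

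The two overlap through *a* but agree only when *b* = *c*. The difference can take either sign. The documents give no value for *b* or *c*.

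**3. Possible size.** The plan's own figures are the Clopper-Pearson limits for the SAE rate in Table 1 (protocol section 3.3.6). The lower limit is the 2.5% quantile of Beta(*x*, *n* − *x* + 1) and the upper limit is the 97.5% quantile of Beta(*x* + 1, *n* − *x*). With *n* = 245, all six rows reproduce; for example, 20/245 gives 8.2% (5.1% to 12.3%). No efficacy rate enters that table.

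The same formula applied to assumed efficacy rates, with one procedure per patient and *n* = 245:

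| Assumed reach | Assumed yield | Gap |
|---|---|---|
| 196/245 = 80.0% (74.4 to 84.8) | 196/245 = 80.0% (74.4 to 84.8) | 0 points |
| 220/245 = 89.8% (85.3 to 93.3) | 184/245 = 75.1% (69.2 to 80.4) | 36/245 = 14.7 points |
| 233/245 = 95.1% (91.6 to 97.4) | 184/245 = 75.1% (69.2 to 80.4) | 49/245 = 20.0 points |

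These rows show a range and do not predict the result. Whether the intervals overlap tells us nothing here, because two different endpoints in the same patients are free to differ.

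**4. The SAP's version of diagnostic yield.** SAP section 3.6 subtracts the proportion with positive prior imaging from the proportion with a diagnosis. With assumed values, 75% − 60% = 15 points, and 70% − 80% = −10 points. Such a figure is not a rate and cannot be compared with the reach rate. The units differ as well: procedures in protocol section 3.1.3, attempts in protocol section 4.1.2, patients in SAP section 3.6. A patient may have a second procedure (protocol section 3.1.2), so these units need not give the same denominator.

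**The case against.** The strongest reply is that little depends on the label. No efficacy endpoint is tested. The only decision rule (SAP sections 2.3 and 3.7.1) and the sample-size reasoning (protocol section 3.3.6) concern the SAE rate. Protocol section 4 leaves the detailed evaluation to the SAP, and SAP section 3.6 has both quantities analysed, so neither can be dropped. All of this stands. A reader might infer a threat to type I error or power from an unsettled main endpoint; the documents do not support that.

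The second reply is that the protocol leans towards diagnostic yield. It is the only quantity that section 3.1.3 formally defines as main, it heads the lists in the summary and section 1.2, and SAP section 3.9 gives it a table of its own (11.2.4). On this view the introductory sentence is simply badly worded. This also stands in part: a reader might infer that the two choices are equally well supported, and they are not. But protocol section 4.1.2 and SAP section 2.3 carry the reach rate and omit yield, and list order is not a stated ranking. The lean does not settle the matter.

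The third reply is that the SAP resolves the conflict by making both secondary. It ranks neither, and it does not withdraw the protocol's label although it is based on that protocol version.

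**Conclusion.** The inconsistency is in the current protocol text and holds without any numerical assumption. Its consequence is confined to reporting: which of two rates, both due to be analysed, is called the main efficacy result could be decided after the data are seen.

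A reader might infer from an illustration such as 90% against 75% that the headline will move by a known amount. It cannot be known. The documents give no expected reach rate or yield, and the assumed gaps above run from 0 to 20 points. Those figures also assume one procedure per patient, 245 patients analysed, and yield expressed as a rate, which SAP section 3.6 at present does not do.

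**What to change.** Before efficacy data are tabulated, name one main efficacy endpoint and use it consistently in the protocol summary, protocol sections 3.1.3 and 4.1.2, and SAP sections 2.3, 2.4 and 3.6. The choice belongs to the sponsor; what matters is that it is made in advance.

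Diagnostic yield is the natural choice, for the reasons given above. In that case:

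- Reword the introductory sentence in protocol section 3.1.3 so that it introduces diagnostic yield.
- Add diagnostic yield to protocol section 4.1.2 and SAP section 2.3, and mark it as the main efficacy variable in SAP sections 2.3, 2.4 and 3.6.
- Report the anatomical success rate as secondary.
- Settle the definition before applying the label. State numerator, denominator and unit using the protocol's percentage of procedures, and replace the difference of proportions in SAP section 3.6, so that the main efficacy result is a rate.

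The cost is wording only. No new data are needed and the sample size does not change. The sponsor gives up the choice of headline.
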